#### CONFIDENTIAL

214066 Protocol Amendment 02

Dose adjustment	Hgb status
To the next lower dose	
 
If the Hgb is >12.0 but ≤12.5 g/dL.         OR
 
the Hgb increased by >2.0 g/dL in 4 weeks.         OR
 
the Hgb increased by >1.0 g/dL in 2 weeks.         Note: if the participant is already on the lowest dose step and requires a dose reduction, withhold dosing and re-check Hgb in 4 weeks, dosing should restart at the lowest dose step when the Hgb is ≤12.0 g/dL.
 

To temporarily stop	If the Hgb is >12.5 g/dL, temporarily withhold dosing and check Hgb at the next study visit in 4 weeks.  Restart at the next lower dose when the Hgb is ≤12.0 g/dL.  Note: From Week 28 if the next study visit is more than 4 weeks from date of test, schedule an extra Hgb check Visit in 4 weeks.  Note: if the participant is already on the lowest dose step at the time of the temporary stop, dosing should restart at the lowest dose step at the next study visit when the Hgb is ≤12.0 g/dL.
No change	Otherwise maintain at the same dose.

The SoA (see Section 1.3) up to Week 28 requires visits every 4 weeks, where Hgb is checked. From Week 28 until Week 52 (when daprodustat treatment ceases), an extra Hgb Visit (at Week 32, 40 or 48) should be conducted 4 weeks after the previous study visit, if any of the following apply:

- At the previous study visit:
  - o A dose change was required (see Table 11).
  - O Dosing was temporarily withheld as follows:
    - Hgb >12.5 g/dL (see Table 11), or
    - the participant was already on the lowest dose in the dose adjustment algorithm and a dose reduction was required (see Table 11 and Section 4.5).
- The following occurs and the next study visit is not due within 4 weeks and a:
  - o Moderate CYP2C8 inhibitor has been prescribed (see Section 6.8).
  - o rhEPO or analogue has been administered in error (see Section 6.8.3).
  - Hgb check performed outside of the study (routine SoC or emergency) indicates that a dose change is needed (see Table 11).
- In the opinion of the investigator, the:
  - o Participant would benefit from continued 4-weekly Hgb checks.
  - Hgb is at the upper end of the target range and waiting 8 weeks for the next Hgb check is considered too long.

In addition to the above, an unscheduled (UNS) Visit at any time during the study may be conducted if, in the opinion of the investigator, the participant would benefit from

214066 Protocol Amendment 02

additional monitoring of Hgb sooner than the next scheduled visit (within 4 weeks) and/or for other parameters or if there is a safety concern. If an UNS Visit is performed, then the UNS electronic case report form (eCRF) pages should be completed. If a dose change is required, then the investigator should urgently contact the medical monitor, who can authorize a manual override of the IRT system to amend the allocated dose.

## 4.7. Role of the IDMC in Confirming the Dosing Strategy

The dosing strategy is expected to be the same in either sub-trial (ND/D) and although their Integrated PK Phases will be analyzed and considered independently, the same review and decision making by the IDMC will be required, see also Section 9.4.1.

The IDMC will be responsible for confirming the decision to open up recruitment for each sequential age group (6 to <12 years, 2 to <6 years and 3 months to <2 years) in turn within each sub-trial, and for confirming the following:

- Starting dose in the next younger age group (Section 4.4.2).
- Upper and lower limits of the common dose adjustment algorithm in these age groups (Section 4.5.2).

The IDMC decision will be based (separately for each sub-trial) on the following:

- PBPK model predictions for adult to pediatric dose scaling, confirmed or updated by the actual PK data analyzed after completion in each age group Integrated PK Phase.
- 4-week Hgb and safety data from each age group's Integrated PK Phase.
- Ongoing Hgb and safety data from all participants in each sub-trial.

For the oldest age group (12 to <18 years), the starting dose and dose adjustment algorithm is already pre-defined as the same as in adults. After the 12 to <18 year PK data in the Integrated PK Phase is available, the appropriate pediatric dose ratio to achieve a matching adult exposure to daprodustat is proposed by the GSK study team and provided to the IDMC (i.e., PBPK model predictions are confirmed or the model updated in light of the actual PK data collected). Assuming no concerns from the review of the Hgb response and safety listings during the Integrated PK Phase of the 12 to <18 years, the IDMC will allow:

- Further recruitment into the Main Study of the 12 to <18 years age group.
- Limited recruitment into the study with the Integrated PK Phase of the 6 to <12 years age group, also confirming the dosing strategy (starting dose and dose adjustment algorithm limits) in this age group.

In turn, once the 6 to <12 year Integrated PK Phase data are available and provided no concerns (from Hgb and safety data from their Integrated PK Phase and from the 12 to <18 years age group also in the trial and available to date), the IDMC will permit recruitment into the Integrated PK Phase for the 2 to <6 years age group and also confirm their dosing strategy (starting dose and limits of the dose adjustment algorithm). Finally,

214066 Protocol Amendment 02

in similar fashion, the youngest age group, the 3 month to <2 years, will be opened to recruitment and their dosing strategy confirmed.

CONFIDENTIAL

#### Requirement for a Protocol Amendment with respect to dosing:

A protocol amendment for dosing will not be produced and the IDMC communication, for both the starting dose and dose adjustment algorithm limits, will serve as the basis for the dosing strategy for the 3 younger age groups provided:

- there are no safety concerns
- the 12 to <18 year age group dosing is confirmed to be the same as for adults, as specified in this protocol for starting dose (see Section 4.4.1) and dose adjustment (see Section 4.5.1),

#### and

and

• for the younger age groups, all doses proposed remain within the limits specified in Figure 4, even if the PBPK model needs updating (revised scaling for the younger age groups).

However, a substantial protocol amendment for approval will be written, and no further recruitment into the study will be permitted until all required approvals for the revised protocol are in place, if the IDMC consider:

 after review of the Integrated PK Phase data that the dosing strategy for the 12 to <18 years needs to be adjusted (i.e., is not the same as adults as specified in this protocol)†,

#### and/or

- after review of the Integrated PK Phase data, that the dosing limits for the 3 younger age groups deviates from that outlined in Figure 4, and/or
- safety concerns are detected.

The IDMC composition, role and format for dosing communications for the 3 younger age groups will be fully described in an IDMC Charter.

## 4.8. End of Study Definition

The end of the study (EOS) Overall is defined as the date of the last visit of the last participant in the study of the last sub-trial (ND or D) to finish. As these sub-trial populations (ND/D) are handled separately within the master basket trial protocol, their last participant visit will differ, particularly if recruitment rate varies between the 2 sub-trial populations. Therefore, an EOS ND and an EOS D is also defined. However, for the purposes of clinical trial disclosure and EOS notification to the Health Authorities

<sup>† Should the dosing strategy for the 12 to <18 years age group need to be adjusted, the protocol amendment will include a requirement for PK collection in a subset of newly recruited participants in that age group who will start with the revised dosing.

TMF-15144431 CONFIDENTIAL

214066 Protocol Amendment 02

and Institutional Review Board (IRB)/Independent Ethics Committee (IEC) the EOS Overall will be used.

With each sub-trial, a participant is considered to have completed:

- the study ("study completer"), if he/she has completed all study visits within their sub-trial (ND or D), including the last Follow-up Visit at Week 56, regardless of whether daprodustat treatment was received during the entire study period.
- study intervention ("treatment completer"), if he/she has not been discontinued prematurely from study intervention (see Section 7.1) and has completed the last required on-treatment visit (Week 52) within their sub-trial, regardless of whether daprodustat treatment was received during the entire study period.

#### CONFIDENTIAL

214066 Protocol Amendment 02

## 5. STUDY POPULATION

This study will enroll patients aged 3 months to <18 years with anemia associated with CKD, within 2 separate sub-trial populations (ND and D). Participants may or may not be receiving treatment with ESAs prior to study entry. Overall, the entire study population describes a group of CKD patients likely to benefit from treatment with daprodustat.

Regardless of their dialysis status, the present study will allow patients not on an ESA with a Hgb level 7.0 to 11.0 g/dL and those receiving treatment with ESA if they have a Hgb concentration of 9.5 to 12.0 g/dL to enroll in the study. The same eligibility criteria apply to both the sub-trials (ND/D) in this study, apart from the requirement for dialysis. Recruitment will close to each sub-trial, and if required within a specific age group, when the requisite number of participants have been enrolled.

The prospective approval of protocol deviations to recruitment and eligibility criteria, also known as protocol waivers or exemptions, is not permitted.

#### 5.1. Inclusion Criteria

The screening period can be up to 4 weeks, although Screening and Day 1 Visits can be performed on the same day. Blood tests for eligibility checked at Screening do not need to be repeated if the Day 1 Visit is performed within 7 days of the Screening Visit.

To be eligible for this study, participants must be offered approach (as determined in Study 212914) and fulfill all of the following criteria at the Screening and Day 1 Visits:

#### Age:

1. Participant must be 3 months to <18 years of age.

Note: Infants born prematurely (under 32 weeks of gestation) should have a chronological age of at least 6 months.

#### Type of Participant and Disease Characteristics:

2. Participants who have anemia associated with CKD as follows:

ND sub-trial	D sub-trial		
CKD stage 3, 4, 5 (not on dialysis) based on eGFR using the bedside Schwartz equation <60 mL/min/1.73m² [Schwartz, 2009]	Prevalent dialysis patients (Stage 5d CKD) defined as those in receipt of maintenance dialysis of ≥30 days duration		
AND			
If not using ESAs, Hgb 7.0 to 11.0 g/dL			
OR			
If using ESAs, Hgb 9.5 to 12.0 g/dL			

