Procedure	Screening (-4 weeks to Day 1)	Day 1	Week 2 (± 3 days)	Week 4 (-7 to +2 days)	Week 8 (-7 to +2 days)	Week 12 (-7 to +2 days)	Week 16 (-7 to +2 days)	Week 20 (-7 to +2 days)	Week 24 (-7 to +2 days)	Week 28 (-7 to +2 days)	Week 36 (-7 to +2 days)	Week 44 (-7 to +2 days)	Week 52 (-7 to +2 days)	UNS at Any Time Day 1 to Week 56 a	4-weekly if needed (Weeks 32, 40 & 48) b	from Study Intervention / Withdrawal Visit	Week 56 (-7 to +2 days)
STUDY INTERVE	NTION	L		l				l			 	l				l	
IRT	Х	Х	Х	Х	Χ	Х	Х	Х	Χ	Χ	Х	Х		X g	Х	Х	Х
Daprodustat dispensing		Х	Х	Х	Х	Х	Х	Х	Х	X	Х	Х		X g	Х		
OTHER																	
Blood transfusion/ iron supplement status	х	Х	Х	Х	X	Х	Х	Х	Х	X	Х	Х	X	X	Х	X	Х
Dialysis modality /transplant status	Х	Х	Х	Х	Х	Х	Х	Х	Х	Х	Х	Х	Х	Х	Х	Х	Х
Concomitant medications	Х	Х	Х	Х	Х	Х	Х	Х	Х	X	Х	Х	Х	Х	Х	Х	Х
Acceptability and Palatability Questionnaire			X														
Complete eCRF	Х	Х	Х	Х	Х	Х	Х	Х	Х	Х	Х	Х	Х	Х	Х	Х	Х

**Abbreviations:** AE = adverse events; BP = blood pressure; BUN = blood urea nitrogen; eCRF = electronic case report form; ECG = electrocardiogram; FOCBP = females of childbearing potential; Hgb = hemoglobin; HR = heart rate; INR = international normalized ratio; IRT = interactive response technology; LFT(s) = liver function test(s); PK = pharmacokinetics; rhEPO = recombinant human erythropoietin; SAE = serious adverse event; TSAT = transferrin saturation; UNS = Unscheduled Visit.

TMF-15144431 CONFIDENTIAL

214066 Protocol Amendment 02

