#### **Rationale for estimand:**

The primary interest lies in the safety of daprodustat for the treatment of anemia associated with CKD for the entire study duration; therefore, the treatment policy strategy is used regardless of disruptions in treatment, treatment delays, intermittent use of rescue therapy and/or unplanned use of ESA therapy, which reflect clinical practice. All safety data will be included up to the end of the period or up to the end of the follow-up period in the analysis irrespective of the occurrence of this ICE. Transition to dialysis (ND subtrial only) is also addressed with treatment policy strategy.

The secondary efficacy interest lies in the Hgb response to oral daprodustat for the treatment of anemia associated with CKD for the entire study duration; therefore, the treatment policy strategy is used regardless of disruptions in treatment or treatment delays, which reflect clinical practice. However, while-on-treatment strategy is used for the ICEs of intermittent use of rescue therapy and/or unplanned use of ESA therapy for the period of 8 weeks following the occurrence of the ICE, since these ICE may confound interpretation of Hgb response to daprodustat. Permanent treatment discontinuation for any reason is also addressed with while-on-treatment strategy.

Transition to dialysis (ND sub-trial only) is addressed with treatment policy strategy.

For participants who undergo a kidney transplantation, data will be considered up to the time of transplantation; therefore, this ICE is addressed with, while-on-treatment strategy. Such participants stop study intervention (daprodustat) and discontinue the study (see Section 7.2). Participants who die during the trial will be addressed with, while-on-treatment strategy.

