### 4.4.2. Starting Dose in the Younger Age Groups:

Assuming the PBPK model predictions are appropriate and unchanged by the PK data collected and analyzed during the study in the Integrated PK Phase, the starting dosing in the younger age groups is also provided in these tables (Table 6, Table 7 and Table 8), based on the predicted scaling (ratio of adult to pediatric dose) in Table 5.

Table 6 Starting Dose of Daprodustat for ESA Non-Users

Baseline Hgb (g/dL)	Daprodustat starting dose per age group (mg, QD)			
	Adults and 12 to <18 years	6 to <12 years	2 to <6 years	3 months to <2 years
<9	4	2	1	0.5
≥9	2	1	0.5	0.25

The lowest clearance (worst case scenario) from the predictions in the respective age groups using different assumptions
of CYP2C8 ontogeny in children. Source: Table 12 GSK Document number 2019N396674\_00

214066 Protocol Amendment 02

Table 7 Starting Dose of Daprodustat in ESA Users, Not on Dialysis

Prior ESA dose at Baseline			Daprodustat starting dose per age group (mg, QD)			
Epoetins (incl	Darbepoetin	Methoxy		(ilig, C	(טאַ	
biosimilars) (convert SC to IV U/week) a	alfa (μg/4wk SC/IV) b	PEG-epoetin beta (µg/month SC/IV)c,d	Adults and 12 to <18 years	6 to <12 years	2 to <6 years	3 months to <2 years
≤2000 e	≤30	≤40	1	0.5	0.25	0.125
>2000 to <20,000	>30 to 300	>40 to 360	2	1	0.5	0.25
≥20,000	>300	>360	4	2	1	0.5

Abbreviations: PEG = polyethylene glycol, SC = subcutaneous, IV = intravenous, U = units

- a. Standard rhEPO IV dose (U/week) = 161/113 x (epoetin SC dose (units))/(frequency) [Besarab, 2002].
- Conversion of 250U:1µg (epoetin IV:darbepoetin alfa) utilized and rounded to the nearest available dose strength [Sterner, 2008].
- Conversion of 1:1.2 μg (darbepoetin alfa:methoxy PEG-epoetin beta) utilized and rounded to the nearest available dose strength [Choi, 2013].
- d. Conversion of 208 U:1 µg (epoetin IV:methoxy PEG-epoetin beta)
- e. This includes ESA users on a zero dose / dose-hold at the time of enrolment

Table 8 Starting Dose of Daprodustat in ESA Users, Undergoing Dialysis

Prior ESA dose at Baseline			Daprodustat starting dose per age group			
Epoetins (incl	Darbepoetin	Methoxy PEG-	• • • • • • • • • • • • • • • • • • • •			
biosimilars) (convert SC to IV U/week) a	alfa (μg/4wk SC/IV)⁵	epoetin beta (μg/month SC/IV) c,d	Adults and 12 to <18 years	6 to <12 years	2 to <6 years	3 months to <2 years
≤2000e	≤30	≤40	4	2	1	0.5
>2000 to <10,000	>30 to 150	>40 to 180	6	3	1.5	0.75

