### **Anemia Related Criteria:**

TMF-15144431 CONFIDENTIAL

214066 Protocol Amendment 02

- 3. Iron deficiency, defined as:
  - Transferrin saturation (TSAT) < 20%, or
  - Ferritin <25 ng/mL.
- 4. Aplasias: History of bone marrow aplasia or pure red cell aplasia.
- 5. Active hemolysis.
- 6. Other causes of anemia: e.g., untreated vitamin B12 deficiency, untreated folate deficiency, thalassemia major, sickle cell disease or myelodysplastic syndrome.

  Note: Sickle cell trait is acceptable if the participant otherwise meets entry criteria.
- 7. GI bleeding: Evidence of actively bleeding gastric, duodenal or esophageal ulcer disease or clinically significant GI bleeding within the last 4 weeks.

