#### 8.2. **Key Definitions**

- Baseline value for any laboratory parameter or vital sign is defined as the last non-missing value prior to the start date and time of the study drug.
- Study day is calculated as the date of event/assessment/specimen collection the first dose of the study drug. One day will be added if resulting study day  $\geq 0$ .
- Duration of any event is defined as end date of the event start date of the event + 1.
- Duration of any event in weeks is defined as (end date of the event start date of the event + 1) / 7, rounded to one decimal place.
- Duration of any event relevant to PK analysis is defined as end date and time of the event start date and time of the event displayed in the format of HHMMSS.
- Change from baseline = post-baseline value baseline value
- Percent change from baseline = (post-baseline value baseline value) / baseline value \* 100
- Pre-treatment phase is defined as any time point prior to the first dose of the study drug, i.e., date <
 date of the first dose.
- On-treatment phase is defined as any time point on or after the first dose of the study drug and on or prior to the last dose of the study drug + 1 day, i.e., date of the first dose ≤ date ≤ date of the last dose + 1 day.
- Integrated PK Phase is defined as the first 4 weeks of dosing in the initially recruited subset of participants in each age group (a minimum of 4 participants per age group; aiming for

This document is confidential

27

SAP Version: SAP V1.0 23-Jan-2025

Effective Date 31-Aug-2020 Controlled Document ID: CC

Page 27 of 59

Statistical Analysis Plan for Interventional Studies

Sponsor: GlaxoSmithKline Research & Development Limited; Protocol No.: 214066/Protocol Amendment 02

approximately 10, 6, 4 and 4 participants for the age groups 12 to <18 years, 6 to <12 years, 2 to <6 years and 3 months to <2 years respectively), during which PK assessments are required.

Post-treatment follow-up phase is defined as any time point within 4 weeks off treatment, i.e., date
of the last dose + 1 day < date ≤ date of the last dose + 28 days.

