### 11.1.2. Handling of Unobserved Data

According Section 7.2, the following ICEs will be handled via while-on-treatment strategy.

- Permanent study intervention discontinuation due to any reason: any unobserved Hgb results
  after study intervention discontinuation will not be considered missing and will not be imputed;
  any observed Hgb results, if collected, will not be included for analysis.
- Unplanned use of ESA therapy: Hgb values within 8 weeks following the unplanned use of ESA
  therapy will be collected but will not be included in the analysis due to ESA's potential
  confounding effect on the interpretation of Hgb response; no imputation will be performed either.
- Intermittent use of rescue therapy (including use of iron supplements [oral/IV/both], blood transfusions and use of ESA and analogues): Hgb values from the date of initial use of rescue therapy until 8 weeks after the last dose of rescue therapy will be collected but will not be included in the analysis or imputed.
- Kidney transplantation or death: unobserved Hgb results after the event will not be considered
  missing and will not be imputed; any observed Hgb results, if collected, after kidney
  transplantation will not be included for analysis.

Disruption in study intervention, delays in study intervention, and transition to dialysis (for ND participants only) will be handled via treatment policy strategy where all observed Hgb results will be included for analysis, but no imputations will be performed for any missing Hgb results.

This document is confidential.

SAP Version: SAP V1.0 23-Jan-2025

Controlled Document ID: CC Effective Date 31-Aug-2020

Sponsor: GlaxoSmithKline Research & Development Limited; Protocol No.: 214066/Protocol Amendment 02

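### Baseline Hgb may be drawn soon after a red-cell transfusion with no flag, although the plan sets aside on-trial Hgb until 8 weeks after one

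*Protocol*

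**What the plan says.** **Entry.** Protocol Section 5.1, criterion 2, sets two Hgb ranges: "If not using ESAs, Hgb 7.0 to 11.0 g/dL" and "If using ESAs, Hgb 9.5 to 12.0 g/dL". Neither depends on transfusion history. Among exclusions 1 to 22 in Section 5.2, the closest are active hemolysis (5), "GI bleeding: Evidence of actively bleeding gastric, duodenal or esophageal ulcer disease or clinically significant GI bleeding within the last 4 weeks" (7), and the investigator's general discretion (22). None names transfusion.

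**Baseline.** SAP Section 8.2 defines the baseline of any laboratory parameter: it "is defined as the last non-missing value prior to the start date and time of the study drug". Protocol Section 4.4 uses baseline Hgb to choose the starting dose for ESA non-users ("Table 6 Starting Dose of Daprodustat for ESA Non-Users"). ESA users are assigned by prior ESA dose (Tables 7 and 8).

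**Transfusion on study.** SAP Section 11.1.2 counts blood transfusion as rescue therapy and leaves out "Hgb values from the date of initial use of rescue therapy until 8 weeks after the last dose of rescue therapy". SAP Section 7.2 limits this to use within the trial. The rationale in Protocol Section 3.2 says that the while-on-treatment strategy applies "for the period of 8 weeks following the occurrence of the ICE, since these ICE may confound interpretation of Hgb response to daprodustat".

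**Data collected.** The Schedule of Activities has a row "Blood transfusion/ iron supplement status", marked at Screening and Day 1. SAP Sections 9.6 and 13.1 put blood products and transfusions in listings. SAP Section 9.4 includes iron use among the baseline disease characteristics, but not transfusion.

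**The concern.** The plan accepts that an Hgb value in the 8 weeks after a transfusion may not be interpretable as a response to daprodustat. A value from the same 8 weeks that happens to precede the first dose becomes the reference for that participant's change from baseline at every visit, and nothing marks it.

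The case is plausible on the protocol's own account. Section 2.2 names transfusion among the existing treatments for this anemia, entry without an ESA is open down to 7.0 g/dL, and Section 8 lets routine blood counts taken before consent serve as screening or baseline values.

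As transfused cells are lost, Hgb falls for a reason unrelated to the drug. In a single-arm trial no control group shares that fall, so it would be read as a weaker response.

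**Working it through.** **1. The plan's own figure.** Protocol Section 9.5.2 gives a precision of 0.4 g/dL (95% CI half-width) for mean change to Week 12, with 50 evaluable participants and an SD of 1.4 g/dL.
- Evaluable: 60 x (1 - 0.17) = 49.8, stated as 50.
- Normal quantile: 1.960 x 1.4 / sqrt(50) = 0.388.
- t quantile, 49 df: 0.398.

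Both round to 0.4, so the figure stands. It serves below only as a yardstick.

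**2. Shift in mean change from baseline.** Let f be the share of participants with a recently transfused baseline and d the lift in their baseline Hgb. Once the lift has gone, the shift is -f x d. Neither input is in the documents. I assume f = 5-10% and d = 0.5-2.0 g/dL.

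| f | d = 0.5 | d = 1.0 | d = 2.0 |
|---|---|---|---|
| 5% | -0.025 | -0.05 | -0.10 |
| 10% | -0.05 | -0.10 | -0.20 |

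Against 0.4 g/dL, the extremes are 0.025 / 0.4 = 6% and 0.20 / 0.4 = 50%. The middle case, 10% at 1.0 g/dL, is 25%.

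**3. With the enrolled number.** The population PK analysis plan issued with the SAP (Section 1.1) says that 4 adolescents were enrolled. One affected participant shifts the mean of all 4 by -d / 4: -0.125, -0.25 and -0.50 g/dL at d = 0.5, 1.0 and 2.0.

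**4. Before the lift has gone.** If a fraction r of the lift remains at a visit, it is present in both values and the shift is -(1 - r) x f x d. Change from baseline is then biased less at early visits, but the Hgb value itself is still raised by the transfusion.

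**5. Which visits the 8-week window reaches.** For a transfusion k days before Day 1, the window ends on about day 56 - k.
- k = 1: day 55. Nominal Weeks 2 (day 14) and 4 (day 28) fall inside.
- k = 28: day 28. Both still fall inside.
- k = 42: day 14. Only Week 2 falls inside.
- k = 55: day 1. Neither falls inside.

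So a transfusion in the 4 weeks before Day 1 covers the baseline and both early visits. Had it been given after Day 1, the SAP would have left out every Hgb value in the following 8 weeks.

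**The case against.** The strongest reply is that the 8-week rule handles an intercurrent event after treatment has started and does not test whether a baseline is valid. The SAP's rescue list also includes iron and ESAs. Carried over literally to baseline, it would set aside ESA users and iron-treated participants whom the design admits on purpose. This stands as a limit: the plan does not contradict its own text, and the extension to baseline should cover red-cell transfusion only. It does not remove the bias, which follows from the baseline definition whatever the status of the 8-week rule.

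Other points also stand in part:
- Participants come from Study 212914, whose criteria are not in these documents and may screen for transfusion. Exclusions 5, 7 and 22 may remove some cases.
- Individual Hgb-and-dose plots and the transfusion listing could reveal a case among 4 participants. Table 2.2 would still include it without a mark.
- The endpoint is secondary and descriptive, and at later visits the bias runs against the drug.

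A reader might infer more than the documents support:
- *That change is understated at all visits.* It is not while the lift persists.
- *That all Hgb endpoints inherit the error.* Hgb value and target range do not use baseline. They are touched only at early visits that still carry the lift.
- *That participants would be wrongly admitted or wrongly dosed.* Table 6 and the transfusion passages in Section 6.8.3 both act on measured Hgb, so no dosing error is shown, and Table 6 concerns ESA non-users only.
- *That a sub-trial mean would move by a known amount.* The split of the 4 between sub-trials is not given.

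**Conclusion.** The concern holds as a minor gap in the SAP. Baseline Hgb carries no condition or flag for recent transfusion, and for an affected participant change from baseline would be understated once the lift has gone.

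Under the assumed 5-10% affected and 0.5-2.0 g/dL lift, the mean shift is -0.025 to -0.20 g/dL. For one affected participant of the 4 enrolled at 1 g/dL it is -0.25 g/dL. Frequency and lift are both assumptions, and nothing in the documents shows that any enrolled participant was transfused before Day 1. The sample-size and precision statements are unaffected.

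**What to change.** In SAP Sections 8.2 and 11.1:

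1. Flag any baseline Hgb drawn within 8 weeks after a red-cell transfusion, using transfusion status at Screening and Day 1 and the blood-product records. Raise a data query where the transfusion date is missing.
2. List the flagged participants, and present Table 2.2 (change from baseline) with and without them.
3. For the same participants, treat Week 2 and Week 4 Hgb inside the 8-week window as the SAP already treats Hgb after an on-trial transfusion. Judge this by actual dates.
4. Do not substitute the last pre-transfusion Hgb. It is likely to sit near a low point, and rebound from it would overstate the response.

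The cost is a few sentences, one flag and one extra display. A few participants would be absent from the sensitivity version of Table 2.2, and some early values would leave the summaries but stay in the listings. Queries may be needed because no look-back period is defined for the transfusion item.

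Recruitment has closed, so a change to the entry criteria would not affect this trial. If the design is reused, the sponsor should reconcile criterion 2 and Table 6 with the transfusion passages. No dose or entry rule is proposed here.
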